#### **8.2.4 Analysis of baseline health conditions**

To assess the overall health of the study patients, the following patient characteristics at baseline will be summarized using number and percentage of patients in each category:

- Clinically significant medical histories by body system;
- Clinically significant current medical conditions by body system;
- Abnormal physical examination findings by body system; and
- Prior/Concomitant medication use at baseline.

“Clinically significant” conditions are whichever conditions that by *a priori* decision of the P.I. may affect the outcome of the islet transplant, including autoimmune diseases, pre-existing CVD, any indications of being at-risk for kidney diseases, and pre-existing mild kidney problems. Current medical conditions will include those conditions reported on the Medical History page of the CRF as current up to the date/time of islet transplant. The remaining conditions reported on the Medical History page of the CRF will be counted in the medical history summary. For the medical history summary, the current medical condition summary and the concomitant medication summary, the percent of patients will be based on the total number of patients in the Safety population. For the physical examination summary, the percent of patients will be based on the number of patients for which the specific body system was assessed. This will include all patients for whom the Normal/Abnormal response is not missing or the response is not reported as ‘Not Done’. The results of physical examination throughout the screening phase up to the immediate pre-transplant work-up will be counted accumulatively. However, more than one abnormality identified for a single patient under the same body system will be counted only once.

For the prior/concomitant medication summary, all medications will be coded to preferred drug names and therapeutic drug class using the World Health Organization (WHO) Drug Dictionary Enhanced. Use of prior/concomitant medications will be summarized for each therapeutic drug class and each preferred drug name. Prior/concomitant medications will include medications that are not part of the treatment regimens (see Section 2.5.) reported on the Current/Prior Medications page of the CRF with a start date/time prior to the date/time of initial islet transplant but indicated as ongoing at the last scheduled visit before the first transplant.

## **9. EFFICACY EVALUATIONS**

### **9.1. Analysis of Primary Endpoints**

The primary endpoint is the proportion of patients with 1) an HbA1c  $\leq$  6.5% at Day 365, AND 2) free of severe hypoglycemic events (for definition see Section 2.7.2a) from Day 28 to Day 365, inclusive, following the first and the last islet transplant, respectively, with the day of corresponding transplant designated Day 0.

#### **9.1.1. Analysis of Primary Endpoints**

The primary analysis is to estimate the true rate of this composite favorable outcome at one year in patients in the ITT population. The proportion of favorable outcomes will be used as the point estimate. An exact (Clopper-Pearson) two-sided 95% confidence interval will be constructed assuming an underlying binomial distribution for the ITT population via SAS:

```
proc freq data=dataset order=freq;  
  
    tables binary_outcome / binomial(exact) alpha=.05;  
  
run;
```

Failure to achieve the favorable outcome will be summarized in two sub-groups: the rate of patients having an HbA1c  $>$  6.5% at Day 365, and the rate of patients who experienced any SHE from Day 28 to Day 365.

The primary endpoint will be assessed for all treated patients from first transplant (including patients with  $>$ 1 transplant within 1 year of first exposure) and from last transplant. A patient's HbA1c results may be reported on visit days that do not fall on the exact Day 365. In this case the records from the date that is the closest to and within 4 weeks (28 days) before or after Day 365 will be used.

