## 2.8. Sample Size and Power Considerations

For the primary endpoint (composite HbA1c  $\leq$  6.5% and absence of severe hypoglycemic events), we expect 80% of the transplant population to achieve this endpoint. Therefore, assuming a sample size of 50, a two-sided 95.0% confidence interval for a single proportion will extend  $\pm$  0.111 from the observed proportion. When the sample size is 40, a two-sided 95.0% confidence interval for a single proportion will extend  $\pm$  0.124 from the observed proportion (Figure 1). Proportion and surrounding confidence interval will be reported.

**Figure 1.** Sample Size Curve for 95% Confidence Interval for Proportion

From recent CITR report, the population rate of favorable outcome under standard insulin treatment for T1D patients indicated as eligible for islet transplant is below 1% (Tiwari et al., 2012). Historical data on islet transplants performed at multiple sites in North America show that the observed favorable outcome rate is at least 70% across all centers. An increase of 50% in the rate of favorable outcome is considered the minimal difference needed to show clinically meaningful benefit. The power of a single-arm trial at a one-sided significance level 0.05 with varying sample sizes and varying observed favorable outcome rates is shown in Table 1.

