**Table 1. Power of a single-arm trial at a one-sided significance level 0.05**

	Sample Size			
	15	20	30	50
Observed Favorable Outcome Rate (%)	Power for the true improvement of the favorable outcome rate to be at least 50% (%)			
65	32	39	51	70
70	50	60	75	91.5
75	71	81	93	99.1
80	88	95	99.2	>99.9

We had planned to enroll at least 50 patients. However, with as few as 15 patients and an observed favorable outcome rate at 80%, we will have 88% of power to show the true treatment effect that at least 50% more of T1D patients than those under standard insulin treatment will attain the favorable outcome through the UIC islet transplantation treatment.

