#### **9.1.2. Treatment of Missing Data**

The primary endpoint should be evaluable for all patients in the ITT population. However missing data can occur due to death, if the patient withdraws consent to be followed, or if immunosuppression is begun but the patient never receives a transplant. In these cases the endpoint will be classified as failure to achieve a favorable outcome. Should the endpoint not be evaluated for a patient for other reasons, a failure will be imputed unless data available at a time longer than one year after transplant indicates otherwise, in which case, that later value will be imputed.

All imputations will be reported in a patient data listing along with the reasons for imputation. The rates and the exact 95% confidence intervals for complete data and imputed data will be compared to ascertain the sensitivity of the imputation.

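### The SAS code in SAP 9.1.1 lets the data choose the event, so the primary estimate and exact interval are for the success rate only when at least half of patients succeed

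*SAP*

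**What the plan says.** SAP 9.1.1 is explicit about the estimand: "The proportion of favorable outcomes will be used as the point estimate". It adds: "An exact (Clopper-Pearson) two-sided 95% confidence interval will be constructed assuming an underlying binomial distribution". Table shell 14.2.1 agrees, since its 95% interval columns are filled only on the Success row.

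The section then prescribes the code. The procedure line is "proc freq data=dataset order=freq" and the request is "tables binary_outcome / binomial(exact) alpha=.05". No level is named, and the SAP does not say how the outcome variable is coded.

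Three other statements bear on size:

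- SAP 2.8 gives the planning rate: "we expect 80% of the transplant population to achieve this endpoint".
- The text under Table 1 allows for a much smaller trial, "with as few as 15 patients and an observed favorable outcome rate at 80" per cent.
- SAP 9.1.2 takes death, withdrawn consent and no transplant after starting immunosuppression, and rules: "In these cases the endpoint will be classified as failure to achieve a favorable outcome". Other unevaluated endpoints are also imputed as failure unless a later value shows otherwise.

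**The concern.** In a one-way PROC FREQ table, `ORDER=FREQ` lists levels by descending count, and `BINOMIAL` without `LEVEL=` analyses the first level listed. Together they make the more common outcome the event. No coding of the variable avoids this, because the order depends only on the counts. The prose fixes the event in advance, whereas the code leaves it to the data.

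At stake is the primary estimate of a Phase 3 trial meant to support a licence application. If fewer than half of patients succeed, following the code literally yields the failure proportion and its interval, and the binomial estimate can never be below 50%. The level is also chosen afresh in each run. The first-transplant and last-transplant columns, or the complete-data and imputed-data comparison in SAP 9.1.2, could therefore describe opposite outcomes.

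**Working it through.** **Inputs.** Expected rate 80%, sample sizes 50 and 40, and a lower illustration of 15 (SAP 2.8 and Table 1); true rates of 65% and 70% as in the rows of Table 1; exact two-sided 95% interval and code (SAP 9.1.1); failure imputation (SAP 9.1.2). The PROC FREQ defaults are taken as standard software behaviour. The documents do not describe them, and SAS was not available to run them.

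**1. The plan's own figure.** SAP 2.8 states: "assuming a sample size of 50, a two-sided 95.0% confidence interval for a single proportion will extend" ±0.111, and ±0.124 at 40. The normal-approximation half-width is 1.96 × √(0.8 × 0.2 / n). This gives 0.1109 at n = 50 and 0.1240 at n = 40. Both figures reproduce.

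**2. What the code returns.** With x successes among n patients, the text asks for x/n and the Clopper-Pearson interval on x. The code gives max(x, n − x)/n and the interval on that count. The limits are the beta quantiles B(0.025; k, n − k + 1) and B(0.975; k + 1, n − k), with k = x for the text and k = max(x, n − x) for the code.

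| Successes | As the text asks | As the code produces |
|---|---|---|
| 40/50 | 80.0% (66.3 to 90.0) | the same |
| 24/50 | 48.0% (33.7 to 62.6) | 52.0% (37.4 to 66.3) |
| 22/50 | 44.0% (30.0 to 58.7) | 56.0% (41.3 to 70.0) |
| 6/15 | 40.0% (16.3 to 67.7) | 60.0% (32.3 to 83.7) |

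**3. How likely a swap is.** The chance is P(X < n/2) for X binomial(n, p).

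| True rate | n = 15 | n = 50 |
|---|---|---|
| 80% | 0.4% | 4.9e-7 |
| 70% | 5.0% | 0.09% |
| 65% | 11.3% | 1.0% |
| 60% | 21.3% | 5.7% |

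**4. Effect of imputing failures.** If a share f of the ITT set is imputed as failure and the success rate among the rest is r, the ITT rate is r(1 − f). It falls below one half when f > 1 − 0.5/r. That is f > 37.5% for r = 80% and f > 28.6% for r = 70%.

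**5. Could a swap create a false claim of benefit?** SAP 2.8 sets the minimal meaningful gain at 50 points over a rate below 1%, so the benchmark is about 50%. In a swapped run with 50 patients, the lower limit is 49.2% when 32 fail and 51.2% when 33 fail. It therefore passes 50% only with 17 or fewer successes. With 15 patients the lower limit is 44.9% when 11 fail and 51.9% when 12 fail, so at most 3 successes are needed. At a true 60%, these counts have probability 0.0002 and 0.002.

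**The case against.** The strongest reply is that nobody could mistake the estimand. The prose names favorable outcomes just before the code, the shell ties the interval to the Success row, and separate rows count the failures. SAS labels the level it analyses, and the one-way table prints both levels with counts and percentages. The code is a short template with placeholder names, and SAP 11.2 requires all programming to be validated before final analysis. Under the planning assumptions a swap is also very unlikely.

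Most of this stands, and it limits the severity. It does not make the prescribed code right, since validation against a specification is weaker when the specification contains the error. The mismatch need not be obvious either: 22 (44) on the Success row beside an interval of 41 to 70 looks plausible, because 44 lies inside it.

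A reader might infer more than the documents support:

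- **That the swap falls exactly where the treatment misses its threshold.** It does not. Judged by the lower exact limit against 50%, 25 to 32 successes of 50 also fall short, and the code is correct throughout that range.
- **That the swap would by itself turn failure into a claim of benefit.** Step 5 of the working shows this needs very low success counts. In neither the 22/50 nor the 6/15 example does the printed lower limit reach 50%.
- **That the secondary endpoints are affected.** SAP 9.2 plans number and percent for the insulin-independence components, shell 14.2.2a has no interval column, and nothing says the binomial code is reused there.

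**Conclusion.** The code and the stated estimand disagree whenever fewer than half of patients succeed. This is a latent specification error, not an expected wrong result. At the planned 80% the output is correct, with a swap chance of about 5e-7 at n = 50 and 0.4% at n = 15. The chance becomes material only if the trial is small and the true rate lower: at n = 15 it is 5.0% at 70% and 11.3% at 65%. Failure imputation can add to it. When a swap occurs the distortion is clear, for example 41.3% to 70.0% in place of 30.0% to 58.7% at 22 of 50.

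The conclusion rests on the standard PROC FREQ defaults, which the sponsor can confirm with one run on dummy data containing a minority of successes. It also assumes that the code is used as written. Severity is minor: a no-cost correction to make before database lock.

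**What to change.** In SAP 9.1.1, remove `order=freq`, state the coding of `binary_outcome` (1 = favorable outcome, 0 = not), and replace the request with:

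`tables binary_outcome / binomial(level='1' exact) alpha=.05;`

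Use this for every run of the primary endpoint: first and last transplant, complete and imputed data. Naming the level is essential. Dropping the frequency ordering alone would put 0 first under 0/1 coding, and the code would then always estimate failure.

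The cost is one changed statement and one sentence on coding. Results with successes in the majority do not change. The secondary endpoints need no change, because they are planned as number and percent only.

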#### **9.1.2. Treatment of Missing Data**

The primary endpoint should be evaluable for all patients in the ITT population. However missing data can occur due to death, if the patient withdraws consent to be followed, or if immunosuppression is begun but the patient never receives a transplant. In these cases the endpoint will be classified as failure to achieve a favorable outcome. Should the endpoint not be evaluated for a patient for other reasons, a failure will be imputed unless data available at a time longer than one year after transplant indicates otherwise, in which case, that later value will be imputed.

All imputations will be reported in a patient data listing along with the reasons for imputation. The rates and the exact 95% confidence intervals for complete data and imputed data will be compared to ascertain the sensitivity of the imputation.

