#### **4. ANALYSIS POPULATIONS**

**ITT population:** Any patient in whom protocol-directed therapy (e.g., pre-transplant immunosuppression) is initiated will be included in the Intent-to-treat (ITT) population. All efficacy analyses will be on this ITT population regardless whether transplantation occurs or not.

**Safety Population:** Any patient in whom protocol-directed therapy is initiated will be included in the Safety population, which is the same as the ITT population. Patients in this population might not receive an islet transplant. All safety analyses will be on this Safety population.

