#### **5. PATIENT ACCOUNTABILITY**

The disposition of patients will be summarized for all patients entered in the clinical database. The following disposition information will be summarized:

- The number and percent of patients who completed the study and the number and percent of patients who were withdrawn;
- The number and percent of patients withdrawing by reason for withdrawal;
- The number and percent of patients not reaching 1 year post first transplant henceforth determined ongoing as of April 13, 2015 and
- The number and percentage of patients included in the Intent-to-treat populations.

All percentages will use the number of patients entered into the database as the denominator. In addition, a data listing of patients withdrawn will be provided and will include for each patient: demographics (age and race), day of withdrawal relative to day of study medication, concomitant medications taken, and reason for withdrawal.

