  - > 200 mg/dl

As with the primary endpoint, the secondary endpoints should be available for all transplanted patients and the analyses will be conducted for the ITT population. If a categorical endpoint is not available for a patient, then it will be treated with the same missing data rules as used for the primary endpoint. If a scalar endpoint is not available for a patient within the designated time window around Day 365, a later value will be imputed if an evaluation is done at a time longer than one year after the final transplant, otherwise the patient will stay missing for the endpoint. If for any endpoints more than 50% of patients do not report data, the endpoints will then not be summarized.

All imputations and missing data will be reported in a patient data listing along with the reasons for imputation and/or missing data.

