- Addition or intensification of antihypertensive therapy
- Oral ulcers
- Lower extremity edema
- Gastrointestinal toxicity (diarrhea)
- Neutropenia (neutrophils < 1.3 thous/ $\mu$ L)
- Anemia (hemoglobin men < 12.1, women < 11.7 g/dL)
- Thrombocytopenia (platelets < 150 thous/ $\mu$ L)
- Infections (viral, bacterial, or fungal)
- Neoplasms, benign or malignant

c. All other TEAEs

The incidence and severity of adverse events reported outside the two aforementioned categories.

The overall summaries will also be done for the following types of AE's:

- SAEs
- TEAEs that lead to discontinuation of the study
- TEAEs resulting in death
- TEAEs graded at least 3 (severe) on the severity scale

In addition to an overall 1-year summary of AEs under each aforementioned category, a summary (number of events and the number and percent of patients having at least one event in the category) by windows of time will be provided for a respective group of AEs after the first transplant: events within the first week (by Day 7), first month (by Day 30), the first three months (by Day 90), the first six months (by Day 180), and the first year (by Day 365). The total number of patients being followed within the specific time window will be used as denominator for calculating the proportion in that time window.

In addition, summaries by SOC and PT will be developed for the following types of AE's:

- TEAEs
- TEAEs reported as related to islet transplantation
- TEAEs reported as having a severe or beyond intensity

The summaries of all TEAEs will present the number of AEs and the number and percent of patients having an AE by SOC and by specific PT. The summary of treatment-related TEAEs and the summary of severe-or-beyond (graded 3-5) AEs will only report the number and percent of patients for each SOC and PT. For the summary of AEs reported as possibly related to islet transplant, missing relationships to the treatment will be counted as possibly related to islet transplant. Likewise, if the maximum severity of an AE is not reported, then the maximum severity of the AE will be imputed.

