**14. TABLE SHELLS**

Protocol: UIH-002  
 Population: All Enrolled

Page x of N

TABLE 14.1.1  
 Patient Disposition and Reason for Early Discontinuation

Disposition [1]	Reason for Early Discontinuation						
	Total n (%)	Death n (%)	Adverse Event n (%)	Consent Withdrawn n (%)	Non- compliance n (%)	Lost to follow-up n (%)	Other n (%)
Completed	XX (XX)						
Early Discont.	XX (XX)	XX (XX)	XX (XX)	XX (XX)	XX (XX)	XX (XX)	XX (XX)
Ongoing	XX (XX)						
Safety Pop.	XX (XX)						

Note: The denominator for all percentages is the corresponding population N.

[1] Disposition as of 1 year after last transplant or April 13th, 2015, whichever occurred first.

XXXXXXXXXX.sas, DDMMYYYY:HHMM

TABLE 14.1.2  
 Demographics and Patient Characteristics

<PAGE 1 FORMAT>

Safety population (N=X)	n	Mean	SD	Median	Minimum	Maximum
Age (years)	X	XX	XX	XX	XX	XX
Weight (kg)	X	XX	XX	XX	XX	XX
Height (cm)	X	XX	XX	XX	XX	XX
BMI (kg/m  )	X	XX	XX	XX	XX	XX

<PAGE 2 FORMAT>

	Race				
	Caucasian n (%)	Black n (%)	Oriental n (%)	Native American n (%)	Other n (%)
Safety population (N=X)	XX (XX)	XX (XX)	XX (XX)	XX (XX)	XX (XX)

	Ethnicity	
	Hispanic n (%)	Non-Hispanic n (%)
Safety population (N=X)	XX (XX)	XX (XX)

	Gender	
	Male n (%)	Female n (%)
Safety population (N=X)	XX (XX)	XX (XX)

XXXXXXXXXX.sas, DDMMYYYY:HHMM

TABLE 14.1.3  
 Baseline Diabetes Control

<PAGE 1 FORMAT>

Safety population (N=X)							
Variable	n	Mean	SD	Median	Minimum	Maximum	Missing n (%)
Insulin Requirement (unit/kg/day)	X	XX	XX	XX	XX	XX	XX (XX)
HbA1c (%)	X	XX	XX	XX	XX	XX	XX (XX)
Frequency of SHE (episodes/month)	X	XX	XX	XX	XX	XX	XX (XX)
HYPO Score	X	XX	XX	XX	XX	XX	XX (XX)
Mixed Meal Test: Fasting Plasma Glucose (mg/mL)	X	XX	XX	XX	XX	XX	XX (XX)
90-min Glucose post glucose challenge (mg/dL)	X	XX	XX	XX	XX	XX	XX (XX)

<PAGE 2 FORMAT>

Safety population (N=X)	n (%) of Patients	Missing n (%)
Reduced awareness of hypoglycemia [1]	X (XX)	X (XX)
Mixed Meal Test: Fasting C-peptide < 0.1 ng/mL [2]	X (XX)	X (XX)
90-min C-peptide post glucose challenge < 0.1 ng/mL	X (XX)	X (XX)

[1] Reported qualitatively only at enrollment.

[2] 0.1 ng/ml is the undetectable lower limit for C-peptide.

XXXXXXXXXX.sas, DDMMYYYY:HHMM

TABLE 14.1.4  
Medical History

Number (%) of Patients with Clinically Significant Medical History Conditions

<PAGE 1 FORMAT >

Safety population (N=X)	Body System				
	Allergy n (%)	Immunology n (%)	Renal/Genitourinary n (%)	Cardio-vascular n (%)	Missing n (%)
	X (XX)	X (XX)	X (XX)	X (XX)	X (XX)

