XXXXXXXXXX.sas, DDMMYYYY:HHMM

TABLE 14.1.5  
 Current Medical Conditions

Number (%) of Patients with Clinically Significant Current Medical Conditions

<PAGE 1 FORMAT>

Safety population (N=X)	Body System				
	Allergy n (%)	Immunology n (%)	Renal/Genitourinary n (%)	Cardio-vascular n (%)	Missing n (%)
	X (XX)	X (XX)	X (XX)	X (XX)	X (XX)

XXXXXXXXXXXX.sas, DDMMYYYY:HHMM

TABLE 14.1.6  
 Screening Physical Examination Results

	Body System					
	Number (%) of Patients with an Abnormality					
	Eyes	ENT	Respiratory	Gastro-intestinal	Genitourinary	Extremities
Safety population (N=X)	X/X (XX)	X/X (XX)	X/X (XX)	X/X (XX)	X/X (XX)	X/X (XX)
	Nervous System	Dermatologic	Lymph Nodes	Endocrine/Metabolic		
	X/X (XX)	X/X (XX)	X/X (XX)	X/X (XX)		

Note: The denominator is the number of patients that had the body system evaluated during the physical exam.

XXXXXXXXXX.sas, DDMMYYYY:HHMM

TABLE 14.1.7  
 Prior/Concomitant Medication Use at Baseline

Drug Class/ Preferred Drug Name	Islet Transplantation (N=X) n (%)
Subj. taking a prior/con. med.	X (XX)
Drug Class 1	
Preferred Name 1.1	X (XX)
Preferred Name 1.2	X (XX)
Preferred Name 1.3	X (XX)
etc.	
Missing	X (XX)

Note: Medications were coded using WHO Therapeutic drug classes and preferred names.

XXXXXXXXXX.sas, DDMMYYYY:HHMM

Table 14.1.8  
 Listing of Islet Infusions by Patients

Total # of Tx Received	Subj. No.	Seq. of Islet Infusion	Date of Islet Infusion
1 Tx	XXX	1	DDMMYYYY
	XXX etc.	1	DDMMYYYY
2 Tx's	XXX	1	DDMMYYYY
	etc.	2	DDMMYYYY
3 Tx's	XXX	1	DDMMYYYY
		2	DDMMYYYY
	etc.	3	DDMMYYYY

XXXXXXXXXX.sas, DDMMYYYY:HHMM

TABLE 14.2.1  
 Summary of Primary Efficacy Endpoint

ITT population (N=X)	Time of Evaluation Number (%) of Patients			
	1 Year after First Tx	(95% C.I.)	1 Year after Last Tx	(95% C.I.)
Success (HbA1c ≤ 6.5% + Free of SHE [1])	X (XX)	(XX, XX)	X (XX)	(XX, XX)
Failure Total	X (XX)		X (XX)	
HbA1c > 6.5%	X (XX)		X (XX)	
Any SHE [1]	X (XX)		X (XX)	
Missing [2]	X (XX)		X (XX)	

[1] SHE occurring between Day 28 and Day 365 (Day 0 being the day of corresponding transplant).

[2] Missing endpoints are imputed as failure.

XXXXXXXXXX.sas, DDMMYYYY:HHMM

TABLE 14.2.2a  
 Summary of Secondary Efficacy Endpoints:  
 Patients Attaining Insulin Independence at 1 Year after First and Last Transplant

ITT population (N=X)	Number (%) of Patients			
	First Tx Day 365		Last Tx Day 365	
	Missing	Missing	Missing	Missing
Absence of exogenous insulin	X (XX)	X (XX)	X (XX)	X (XX)

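### SAP 9.1.2 would score patients not yet at one year as failures if the 13 April 2015 cut-off governs efficacy, and its later-value exception admits an HbA1c taken after a further infusion

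*SAP*

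**What the plan says.** SAP 9.1.2 expects the primary endpoint to be evaluable for everyone in the ITT population. It names three sources of missing data that count as failure: death, withdrawal of consent to follow-up, and immunosuppression started without a transplant. It then adds a catch-all: "Should the endpoint not be evaluated for a patient for other reasons, a failure will be imputed unless data available at a time longer". The exception is a value obtained beyond one year that points the other way; it then replaces the imputed failure. The footnote to the Table 14.2.1 shell says "Missing endpoints are imputed as failure". That shell has success, failure and missing rows, and none for ongoing patients.

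SAP 4 fixes the denominator: "All efficacy analyses will be on this ITT population regardless whether transplantation occurs or not".

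SAP 5 will report "The number and percent of patients not reaching 1 year post first transplant henceforth determined ongoing as of April 13, 2015". The Table 14.1.1 shell has an Ongoing row but counts from a different infusion: "Disposition as of 1 year after last transplant or April 13th, 2015, whichever occurred first". SAP 2.7.1 and SAP 10 attach the same date to safety follow-up. SAP 9 gives no date for efficacy.

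Incomplete follow-up is handled for adverse events by time window. In SAP 10.1.5, "The total number of patients being followed within the specific time window will be used as denominator".

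For a categorical secondary endpoint that is unavailable, SAP 9.2 says "it will be treated with the same missing data rules as used for the primary endpoint". For a scalar endpoint, "a later value will be imputed if an evaluation is done at a time longer than one year after the final transplant". Protocol 6.5.1 allows further infusions in the first year after the last infusion and throughout the 5-year follow-up.

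**The concern.** There are two separate problems, and they bias the result in opposite directions.

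The first concerns patients who have simply not been followed long enough. Being short of one year is not one of the three named reasons, so only the catch-all reaches these patients. The later-value exception cannot rescue them, because no value beyond one year exists yet. If efficacy is cut on 13 April 2015, they become failures because of their enrolment date and not because of anything the treatment did. SAP 9.1.1 sets out to estimate the true rate of favourable outcome, and that estimate would then depend on calendar time.

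The second needs no assumption about the cut-off. The later-value exception has no upper time limit and says nothing about intervening treatment. A missing HbA1c one year after the first infusion could be filled by one measured after another infusion given beyond Day 365. The endpoint labelled as one year after the first infusion would then partly reflect treatment given after that year. SAP 9.2 has a related fault: it ties later scalar values to the final transplant even when the time point is defined by the first.

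**Working it through.** **The plan's own precision figures.** SAP 2.8 expects 80% and gives half-widths of 0.111 at N=50 and 0.124 at N=40. The normal approximation gives 1.96 × √(0.8 × 0.2/50) = 0.1109 and 1.96 × √(0.8 × 0.2/40) = 0.1240, so both are reproduced. The intervals below use the exact Clopper-Pearson method that SAP 9.1.1 prescribes for the analysis.

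**Ongoing patients scored as failures.** Inputs are the 80% rate (SAP 2.8), N=50 (planned) and N=15 and 20 (sizes in SAP Table 1). The number ongoing, k, is an assumption because the documents do not give it. The expected rate is 80% × (N − k)/N, so the loss per ongoing patient is 80/N points: 80/50 = 1.6, 80/20 = 4.0, 80/15 = 5.3. With k=2 of 50 the expected rate is 80% × 48/50 = 76.8%.

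| N | k | Ongoing counted as failures (exact 95% CI) | Ongoing left out (exact 95% CI) |
|---|---|---|---|
| 50 | 0 | 40/50 = 80.0% (66.3–90.0) | same |
| 50 | 5 | 36/50 = 72.0% (57.5–83.8) | 36/45 = 80.0% (65.4–90.4) |
| 50 | 10 | 32/50 = 64.0% (49.2–77.1) | 32/40 = 80.0% (64.4–90.9) |
| 20 | 5 | 12/20 = 60.0% (36.1–80.9) | 12/15 = 80.0% (51.9–95.7) |
| 15 | 5 | 8/15 = 53.3% (26.6–78.7) | 8/10 = 80.0% (44.4–97.5) |

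**Dates.** 13 April 2015 minus 365 days is 13 April 2014, the last first-infusion date that reaches Day 365 by the cut-off. SAP 9.1.1 accepts an HbA1c within 28 days either side of Day 365, that is Day 337 to Day 393. 13 April 2015 minus 393 days is 16 March 2014. For first infusions from 17 March to 13 April 2014 the window is therefore still open at the cut-off.

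**Insulin independence.** SAP 9.2 and the Table 14.2.2a shell report it among all patients and among those attaining the primary endpoint. An ongoing patient scored as a failure stays in the first denominator and drops out of the second. Only the all-patients line is lowered.

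**Later values.** Success needs HbA1c ≤ 6.5% at Day 365 and no severe hypoglycemic event from Day 28 to Day 365 (SAP 9.1). The exception reaches a patient whose Day 337–393 HbA1c is missing, who has a further infusion after Day 365, who has a favourable HbA1c after that infusion, and who meets the hypoglycemia component. Protocol 6.6.7 restarts the visit schedule at a second or third transplant, so an HbA1c near Day 365 from the first infusion is not assured in re-infused patients. The last-infusion rate is unaffected, because a further infusion would redefine which infusion is last.

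**The case against.** The strongest answer is that the first problem may never arise. No sentence applies 13 April 2015 to efficacy. SAP 9.1.2 expects the endpoint to be evaluable for all ITT patients, and SAP 11 plans no interim analysis and one final analysis after database lock. All of that fits an efficacy analysis run once everyone has passed one year. A reader might infer that ongoing patients will be scored as failures; the documents support this only as a conditional. Nor do they suggest that 5 or 10 patients were ongoing.

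A reader might also infer that the SAP has no rule for these patients. It has one: the catch-all makes them failures. Counting missing as failure in the full ITT set is a recognised conservative choice for a single-arm trial. SAP 9.1.2 also plans rates and exact intervals for complete and imputed data side by side, with every imputation and its reason listed. That would expose the effect. But the comparison pools ongoing patients with deaths and withdrawals, and leaves the Table 14.2.1 rate unchanged.

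On later values, it is tempting to say that a favourable late HbA1c turns a missing result into a success. It does not by itself, because the Day 28–365 hypoglycemia component must still be met. Re-infusion within the first year is accepted by design in SAP 9.1.1 and is not at issue. The documents also plan some assessments one year after the first transplant, such as continuous glucose monitoring, so contact at that time is likely, although HbA1c is not named there.

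**Conclusion.** The point holds in two parts and should be fixed before analysis.

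The ongoing-patient part is conditional on the cut-off applying to efficacy. If it does, the expected loss is 80/N points per ongoing patient at an assumed 80% true rate, for a number of patients that is unknown and may be zero. It is small at N=50 with one or two ongoing, and large if the analysis is near the 15 patients that SAP 2.8 calls sufficient. The direction is against the treatment. A reader might infer that every insulin-independence result falls too; only the all-patients line does.

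The later-value part rests on no such assumption. It concerns the first-infusion time point only, is probably infrequent, and biases upward. Its frequency cannot be estimated from the documents.

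SAP 5 and Table 14.1.1 also define ongoing from different infusions. A patient past one year from the first infusion but not from the last is ongoing under one and not the other. Confidence is medium, because the first part depends on an unstated analysis date.

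**What to change.** **Later values.** In SAP 9.1.2, accept a later value for the first-infusion time point only if it was taken before any further infusion after Day 365. In SAP 9.2, anchor the later value to the transplant that defines the time point.

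**Cut-off.** State whether 13 April 2015 applies to efficacy. If it does:
- Base the main first-infusion rate on ITT patients whose first infusion (or therapy start, if never infused) was on or before 13 April 2014. The set is then defined by date and not by outcome.
- Where the HbA1c window is still open at the cut-off, use any value already within it; otherwise the ordinary 9.1.2 rule applies, with the reason listed.
- Keep death, withdrawal and no transplant as failures within this set.
- Report later patients in an Ongoing row of Table 14.2.1, outside the denominator, and list any deaths or severe hypoglycemic events already seen in them.
- Use the same set for the all-patients insulin-independence line.
- Show the all-ITT failure-imputed rate as a sensitivity analysis.

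**Last-infusion rate.** Reconcile the two definitions of ongoing. Keep the all-ITT failure-imputed figure as the main one, with the complete-data figure beside it, because recently re-infused patients are a selected group.

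**Cost.** SAP wording and one table row, with no new visits or data. The smaller denominator widens the first-infusion interval: 26.6 points at 32/40 against 23.7 at 40/50. Early failures among ongoing patients would appear only in the sensitivity analysis and the listing.
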